2.3.2 Benefit Assessment

The purpose of this Phase II, proof-of-concept clinical study is to evaluate the efficacy, safety and tolerability of AZD1402 in adult participants with asthma on medium-to-high dose ICS-LABA. For participants randomised to AZD1402, there is a potential benefit in terms of improvement of their asthma status as indicated by a reduction in the lung inflammation biomarker FeNO seen in Phase I studies. Participants may derive benefit from health assessments (eg, ECG, clinical laboratory safety measurements, and standard of care adherence monitoring) performed as part of the study.

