All confidence intervals (CIs) will be 2-sided 95% CIs, unless stated otherwise, and presented to one more decimal place than the raw data recorded in the database. If a model is used to estimate the treatment difference, the corresponding CI according to the model will be presented. Otherwise, the unadjusted CI will be used. Nominal p-values may also be presented. Care should be taken when interpreting CIs and p-values since no correction for multiple testing is done for the endpoints.

P-values greater than or equal to 0.001, in general, will be presented to 3 decimal places. P-values less than 0.001 will be presented as “<0.001”.

Descriptive statistics for calculated PK parameters and FeNO will include: n , mean, SD, geometric mean, geometric coefficient of variation (GeoCV%), median, minimum and maximum values.

The GeoCV% will be calculated as $SQRT(es^2-1)*100$ where s is the SD of the log-transformed values.

Daylight saving dates will be considered in the calculation of the absolute scheduled and actual times and in the duration when this is based on times. Therefore, if any daylight saving change occurs during the study development, this will impact the description of the blood sample collections, the calculation of the PK parameters and any AE duration in case the time is included in the calculation of the duration.

Statistical Analysis Plan

All other requirements and specifications for programming and presentation of TFLs will be specified in the TFL shells document.

The following rules will be applied for any repeated safety assessments:

- For repeated assessments at any timepoint before first IP administration (including screening values and baseline): the latest assessment obtained per timepoint will be used in the calculation of descriptive statistics.
- For repeated assessments at any timepoint after first IP (including Follow-up visit): the first (non-missing) value after dosing will be used in the calculation descriptive statistics.

The AM and PM assessments will be combined into a daily assessment according to the following formula:

Let assessment (Day i) = (PM assessment (Day i) + AM assessment Day (i+1)) / 2

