In case of missing values among the measurements defining the baseline of the e-Diary variables, the baseline will be defined as the mean of all available measurements in the 7 days period. In all other cases of missing values in measurements defining a baseline, the baseline value will be defined as the last non-missing value prior to Day 1.

Change from baseline will be defined as the value post-dosing minus the baseline defined, for each timepoint.

Percent change from baseline will be calculated as:

- Percent change from baseline = ((visit value – baseline value)/baseline value) ×100%

The average change from baseline over the treatment period will be calculated from the subjects' average measurements of all assessments performed while subjects are on-treatment, minus the baseline value.

If either a visit value or the baseline visit value is missing, the absolute change from baseline value and the percent change from baseline will also be set to missing.

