4.12.3 PEF and Asthma Symptoms Score

A summary by treatment group (different doses of AZD1402, pooled AZD1402 and placebo) in terms of absolute values at baseline and average over the treatment period, as well as change from baseline and its average over the treatment period, will be presented for average morning PEF, average evening PEF and in daily average asthma symptom score (AM/PM).

The average morning PEF will be calculated as:

(sum of morning PEF values in treatment period) / (number of morning e-Diary sessions completed during period).

The average evening PEF will be calculated analogously.

Statistical Analysis Plan

Daily asthma symptom score for day n will be the average of the evening score recorded for day n and the morning score for day n+1.

The average daily asthma symptom score will be calculated as:

(sum of daily values in treatment period) / (number of calculated daily values during period).

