4.12.4 Fractional Exhaled Nitric Oxide

The analysis of change from baseline in log transformed FeNO will be performed as described for the primary endpoint in Section 4.11. These analyses will be done on the natural log scale and the results will be back-transformed to linear scale. Hence treatment effects will be presented in terms of Geometric LS means (GeoLSMeans) and treatment differences and associated CIs will be presented in terms of GeoLSMeans ratios. Due to the log-transformation, the GeoLSMeans represent a relative change from baseline rather than an absolute change from baseline.

Percentage change from baseline in FeNO at each week and average over the treatment period will be summarised by treatment group and the following summary statistics will be presented: n, geometric mean, GeoCV (%), median, minimum, and maximum.

For repeated follow-up post-baseline measurements that are taken on the same day and time as a scheduled visit and time point, the average response value of the morning assessments will be used. The average over the treatment period will be calculated from the subjects' average measurements of all assessments performed whilst subjects are on-treatment between Visit 3 and Visit 7.

All the efficacy variables will be presented in listings.

The following figures will be presented:

[figure not shown]
- In-clinic FeNO, individual subject data over time.
- Mean FeNO in-clinic absolute values (ppb) by week
- Mean FeNO in-clinic percentage change from baseline by week
- GeoLSMeans of the ratio (post/baseline) (+/- SE) in FeNO over time within each treatment group will be provided.

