4.17.6 Fractional Exhaled Nitric Oxide

Fractional exhaled nitric oxide will be listed by subject and timepoint including the date/time of the assessment, percentage changes from baseline and repeat/unscheduled measurements.

Descriptive statistics (n, mean, SD, median, minimum, maximum) for absolute values and percentage changes from baseline will be presented by treatment group (AZD1402 and placebo) and by pooled AZD1402 groups.

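### SAP 4.12.4 asks for a geometric mean and GeoCV of percentage change in FeNO, which are undefined once any participant's FeNO is unchanged or falls; the PEF denominator in SAP 4.12.3 can be aligned in the same edit

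*SAP*

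**What the plan says.** **FeNO.** SAP 4.12.4 names the variable, "Percentage change from baseline in FeNO at each week and average over the treatment period will be summarised by treatment group", and then its statistics: "the following summary statistics will be presented: n, geometric mean, GeoCV (%), median, minimum, and maximum". Two definitions elsewhere in the SAP govern that request. SAP 4.6.1 gives "Percent change from baseline = ((visit value – baseline value)/baseline value) ×100" (expressed as a percentage). SAP 4.2 gives GeoCV as √(exp(s²) − 1) × 100, "where s is the SD of the log-transformed values".

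The rest of SAP 4.12.4 works on a valid scale. The model is fitted to log FeNO and back-transformed, and one planned figure shows "GeoLSMeans of the ratio (post/baseline) (+/- SE) in FeNO over time". SAP 4.17.6, the safety summary of FeNO, uses arithmetic statistics: "Descriptive statistics (n, mean, SD, median, minimum, maximum) for absolute values and percentage changes from baseline will be presented by treatment group".

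**PEF.** SAP 4.12.3 defines the average morning value over treatment as "sum of morning PEF values in treatment period) / (number of morning e-Diary sessions completed during period", with evening PEF handled the same way. In the same section the average daily symptom score is divided by the number of daily values actually calculated. SAP 4.6.1 bases the e-Diary baseline on available measurements, and the on-treatment average on the assessments performed. SAP 4.10.3 rules out imputation apart from some adverse-event dates.

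**The concern.** A geometric mean and a GeoCV exist only for positive quantities. Percentage change in FeNO is positive only for participants whose FeNO rose. Protocol 2.3.2 bases the potential benefit on "a reduction in the lung inflammation biomarker FeNO seen in Phase I studies", so the requested statistics fail in the direction the treatment is meant to produce. They will also fail in the placebo arm, where some values can be expected to drift down. In-clinic FeNO at Week 4 and averaged over treatment is a named secondary endpoint, so the table will be read, and its programmer has no stated rule for non-positive values.

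The PEF formula raises a lesser question. Numerator and denominator count different things. If a diary session is complete but holds no PEF value, it adds nothing to the sum and one to the count, which is the same as entering 0 L/min. The baseline is a mean of available values and has no such penalty, so change from baseline would be pushed downward. Morning and evening PEF are also named secondary endpoints, although this SAP only describes them.

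**Working it through.** The documents give no FeNO or PEF result to reproduce, so the check applies the SAP's own formulas to assumed values.

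**FeNO**

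1. Assumed values for six participants (ppb): baseline 40, 50, 30, 60, 45, 80; post-baseline 32, 50, 36, 48, 54, 60.
2. Percentage change by SAP 4.6.1: −20, 0, +20, −20, +20, −25.
3. Four of the six have no logarithm, so s in the GeoCV formula does not exist, nor does the log-scale mean behind the geometric mean.
4. Ratio post/baseline: 0.80, 1.00, 1.20, 0.80, 1.20, 0.75. The product is 0.6912 and its sixth root is 0.940, so the change is (0.940 − 1) × 100 = −6.0%. GeoCV of the ratios is 21.5%. All six participants contribute.
5. How often would the request be computable? Every participant in the cell must rise. With an assumed 0.5 chance of a rise each, that is 0.5⁵ = 0.031 for 5 participants and 0.5⁸⁰ ≈ 8 × 10⁻²⁵ for 80 (the planned Part 2 arm sizes are 5, 80 and 80). With an assumed 0.3 chance, it is 0.3⁵ = 0.0024 for 5.

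Purely as a hypothetical, suppose undefined logs were silently dropped. Take a true geometric mean ratio of 0.7 (a 30% fall) and a log-ratio SD of 0.3, 0.4 or 0.5, all assumed. The share retained is Φ(ln 0.7 / SD) = 11.7%, 18.6% or 23.8%. By simulation, the geometric mean of the retained percentage changes is +9.7%, +15.2% or +21.5%. The SAP does not prescribe this step.

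**PEF**

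1. With true mean P, S completed sessions and m of them without a reading, the SAP 4.12.3 average is P × (S − m)/S, an error of −P × m/S.
2. Assume S = 27 mornings (Days 2 to 28) and m = 1. The error is −9.3, −13.0 or −16.7 L/min at P = 250, 350 or 450 L/min. With S = 28 and P = 350 it is −12.5 L/min.
3. With one such session in every participant and balanced baselines, a true between-arm difference shrinks by 1/27 = 3.7%.
4. If m = 0, the error is zero.
5. Dividing by the number of non-missing readings returns P for any m.

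**The case against.** **On FeNO**, the best defence is that nobody would be misled. SAP 4.12.4 already works with logs, back-transformation and a post/baseline figure, so a programmer would probably compute the geometric mean ratio and show it as a percentage. TFL shells that are not available here may say so. The information is also largely covered elsewhere: model-based ratios with confidence intervals, a figure of mean percentage change by week, arithmetic mean and SD in SAP 4.17.6, and mean and SD for FeNO summaries in SAP 4.2. This is fair on consequence and keeps the point minor. It does not rescue the text, because no passage supplies a ratio-then-convert step for this table. A reader might go further and infer that the plan would report a rise where FeNO fell. The documents do not support that: dropping non-positive values is a programming choice the SAP never states.

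**On PEF**, the defence is stronger. Protocol 8.1.4 lists PEF among the daily diary assessments, and Protocol 8.1.11 has the reading captured as the diary entry concludes. Sessions and readings may therefore coincide. The statement in Protocol 8.1.11 and SAP 3.2.1.1 that PEF follows completion of the diary may describe only the order of steps. SAP 4.6.1 already states the right rule for the average. All of this stands.

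A reader might also infer that PEF is missing by design on every clinic morning, because footnote o to Protocol Table 2 limits home spirometry to non-clinic timepoints. The documents do not bear that out. SAP 4.6.1 includes the Day 1 pre-dose value in baseline morning PEF although Day 1 is a clinic visit. Table 2 marks the home device at Visits 3 to 7, and Protocol 8.1.11 asks for morning PEF on waking.

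**Conclusion.** **FeNO: wrong as written, minor.** The geometric mean and GeoCV of percentage change are undefined for any treatment group and week with one participant whose FeNO is unchanged or lower. On any realistic assumption that is practically every cell of the table. This conclusion rests only on the SAP's own definitions; the assumed numbers merely illustrate it. The damage is confined to two statistics in one descriptive table.

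**PEF: an inconsistency to tidy, with no demonstrated error.** The session denominator disagrees with SAP 4.6.1 and SAP 4.10.3 and would treat a completed session without a reading as zero. Whether such a session can exist depends on what counts as completed, which the documents leave open. The effect may be nil. If it is not, the size is about 13 L/min per affected session under the assumptions above.

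Neither matter touches the primary FEV₁ analysis.

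**What to change.** In SAP 4.12.4, state that the geometric mean and GeoCV are computed on the ratio of post-baseline to baseline FeNO, and that the geometric mean is displayed as (geometric mean ratio − 1) × 100%. Median, minimum and maximum of percentage change can stay as they are. This puts the table on the same scale as the ratio figure already planned there.

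In SAP 4.12.3, divide by the number of non-missing morning (or evening) PEF values in the treatment period. This agrees with SAP 4.6.1 and is correct under every meaning of a completed session. The cough VAS average in SAP 4.13.3 uses the same session count and can be aligned with that section's own sentence about averaging all assessments; it is not a separate error.

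The cost is a few lines of SAP text and derivation code, with no new data.

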4.13 Exploratory **CCI** Variables (Part 1)

All the exploratory analysis will be presented based on FAS. The exploratory efficacy variables will be evaluated with descriptive statistics. All the efficacy variables will be presented in listings

4.13.1 **CCI**

CCI

CCI

CCI

CCI

CCI

4.13.2 Fractional Exhaled Nitric Oxide

A summary by treatment group (different doses of AZD1402, pooled AZD1402 and placebo) in terms of absolute values (ppb) at baseline (Visit 3) and at each day during treatment as well as the average over the treatment period, will be presented. Moreover, change from baseline at each visit during treatment and over the treatment period will be calculated as % change from baseline.

The average over the treatment will be calculated from the subjects' average measurements of all assessments performed whilst subjects are on-treatment.

Fractional exhaled nitric oxide (ppb) assessments will also be listed.

For FeNO at home assessments, the same summary described above for FeNO test (in-clinic assessments) will be presented. The average over the treatment will be calculated as the average of all assessments measurements for a given subject during the treatment period.

For repeated post-baseline FeNO test measurements that are taken on the same day and time as a scheduled visit and time point, the average response value of the morning pre-dose will be used.

For repeated post-baseline FeNO at home measurements that are taken on the same day and time, the highest results of the morning pre-dose will be used.

The following figures will be presented:

- In-clinic FeNO, individual subject data over time.
- Mean FeNO in-clinic absolute values (ppb) by day
- Mean FeNO in-clinic percentage change from baseline by day

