4.6.1 Baseline, Change from Baseline and Percentage Change from Baseline Definitions

In general, the baseline which will be used in calculation of change from baseline will be the last value obtained before first study intervention.

Exceptions to the general definition of baseline (for calculation of change from baseline) are the following:

- In-clinic FeNO test: baseline is defined as the mean of measurements at Day -1 and at Day 1 morning pre-dose at Visit 3 in Part 1 and as Day 1 morning pre-dose at Visit 3 in Part 2.
- FeNO at home assessments: baseline is defined as the mean of all available measurements during the 7 days period prior to Day 1 in Part 1.
- In-clinic pre-bronchodilator FEV₁, FVC and FEV₁/FVC in absolute values and in percent of predicted values: baseline for Part 1 is the mean of measurements at Day -1 and at Day 1 morning pre-dose at Visit 3; for Part 2 is the pre-bronchodilator assessment at Visit 1.
- In-clinic FEV₁ is the mean of Day -1 and Day 1 morning pre-dose at Visit 3 for Part 1 and is the mean of measurements at Day 1 pre-dose timepoints (15 and 45 minutes pre-dose) for Part 2.
- In-clinic post-bronchodilator FEV₁, FVC and FEV₁/FVC in absolute values and in percent of predicted values: baseline is the measurement at Visit 1 (1 measurement) within performed 15 to 30 minutes after inhalation of 400 µg of salbutamol.
- FEV₁ home spirometry: baseline is defined as the mean of all available measurements during the 7 days period prior to Day 1 in both Part 1 and Part 2. i.e. The baseline for the morning assessments will be: the mean of all available morning measurements in the 7 days period prior to Day 1. Same approach will be used for the baseline for the evening assessments.
- e-Diary variables (cough VAS, **CCI** [REDACTED], evening PEF, daily asthma symptom score): baseline is average over measurements on the 7 days prior to randomisation. For the morning assessments of PEF, daily use of rescue medication and asthma symptoms the baseline is average over morning assessments from Day -6 to Day -1 and the Day 1 pre-dose assessment.

For e-Diary any study day will be derived relative to randomisation.

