i Vital signs to be performed BID whilst participants are in-clinic. Vital signs will be measured pre-dose at the scheduled morning dose in-clinic visits and additionally prior to the evening dose if participants receive the evening dose at the clinic (eg, due to optional overnight stay).

j Refresher training as required.

k Rescue medication to be as necessary. Check if participant has enough rescue medicine for use at-home use and refill if necessary.

l FeNO will be measured pre-spirometry, pre-dose (as applicable), and pre-bronchodilation.

m FeNO assessments at home will only be performed (morning and evening) at non-clinic visit timepoints.

n In-clinic spirometry on Days 1 to 14 and Day 28 will be performed pre-dose and 2 h post-dose (\pm 15 min) in the morning (prior to taking controller medication) and on Days 1 to 13 pre-dose and 4 h post-dose (-2 h) in the evening. Where possible, all post-randomisation morning pre-dose clinic spirometry assessments should be performed within \pm 30 minutes of the time that the randomisation spirometry was performed during the residential period. The evening pre-dose spirometry should also be performed within a \pm 30 minutes window relative to the evening assessment timepoint. If patients remain in the unit without discharge to stay overnight during Days 14 to 27, a pre-dose and 2 h post-dose spirometry assessment will be performed in the morning (prior to taking controller medication) and pre-dose and 4 h (-2h) post-dose spirometry assessment in the evening. If patients are discharged and re-admitted to the unit for overnight stay on Days 15 to 27, the morning and evening post-dose spirometry assessment will be 4 h (-2h) post-dose (controller medication timing will remain unchanged from home dosing and controller medication will be taken directly after study intervention). At clinic visits with no overnight stay, morning pre-bronchodilator and 2 h post spirometry will be performed. The timing of controller medication and clinic post-dose spirometry assessments may be adjusted by the Sponsor.

o ECG will be measured before (within 75 min) and 1 hour (\pm 10 min) after administration of study intervention on visits as indicated.

p Home device spirometry will be performed pre-dose twice daily, including on in-clinic assessment days. On in-clinic assessment days, home spirometry may be performed up to 2 hours prior to dosing.

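### Part 1 home FeNO: repeat readings keep the highest value after baseline but are set against a baseline mean, which shifts percentage change slightly upward in sessions with repeats

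*SAP*

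**What the plan says.** SAP 4.13.2 has two rules for repeated post-baseline FeNO readings in Part 1. For in-clinic repeats, "the average response value of the morning pre-dose will be used". For home readings that share a day and time, "the highest results of the morning pre-dose will be used". Part 2 has in-clinic FeNO only, and SAP 4.12.4 averages there too: "the average response value of the morning assessments will be used". Home FeNO in Part 1 is thus the only FeNO measure for which a maximum is taken.

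No maximum applies at baseline. SAP 4.6.1 states: "FeNO at home assessments: baseline is defined as the mean of all available measurements during the 7 days period prior to Day 1".

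Part 1 FeNO is summarised by treatment group on a relative scale: "change from baseline at each visit during treatment and over the treatment period will be calculated as % change from baseline". For the home period average, SAP 4.13.2 says: "The average over the treatment will be calculated as the average of all assessments measurements for a given subject during the treatment period". It does not say whether the highest-value rule is applied first. SAP 5.1 limits when home readings are taken: "FeNO assessments at home will only be performed (morning and evening) at non-clinic visit timepoints". SAP 4.13 makes the Part 1 exploratory analyses descriptive, and SAP 4.10.1 plans no hypothesis test in Part 1.

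**The concern.** A change from baseline should process the measurement in the same way before and after treatment starts. Here a repeated session contributes its maximum after baseline, while every baseline reading enters a mean. The maximum of several readings is never below their mean, so each repeated session with unequal readings pushes percentage change upward. Nothing offsets this at baseline.

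The direction matters because Protocol 2.3.2 describes the potential benefit as a fall in FeNO. Part 1 is read descriptively, arm by arm, so a shift in the within-arm percentage change goes straight into what the reader sees.

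The SAP gives no reason for the rule. Its wording closely follows the home spirometry rule in SAP 4.17.5, so it may have been carried over, though that cannot be shown. Taking the best attempt has an obvious logic for an effort-dependent test; Protocol 8.1.11 does so for PEF. Protocol 8.1.3 describes FeNO as a concentration measured at a standardised exhalation flow and does not discuss repeats.

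**Working it through.** The plan gives no figure on this point, so there is none to reproduce. It also gives no within-session variability and no repeat rate. The following are assumptions: within-session CV 5% to 10%, two or three readings when a session is repeated, 10% to 30% of mornings repeated, and day-to-day CV 20%.

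**Per repeated session.** For k independent, roughly normal readings, the expected maximum exceeds the mean by 1/√π = 0.564 SD (k = 2) or 3/(2√π) = 0.846 SD (k = 3). Multiplying by the CV:
- k = 2, CV 5%: 0.564 × 5% = 2.8%
- k = 2, CV 10%: 0.564 × 10% = 5.6%
- k = 3, CV 5%: 0.846 × 5% = 4.2%
- k = 3, CV 10%: 0.846 × 10% = 8.5%

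This is the range of about 3% to 8%.

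**In the mean.** Only repeated mornings are shifted, so the shift in the mean is about the share repeated times the figure above. The extremes are 10% × 2.8% = 0.3 points and 30% × 8.5% = 2.5 points.

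**Simulation.** Each scenario used 20,000 participants, a baseline averaged over 14 single-reading sessions in 7 days, and 13 post-baseline mornings. Entries are mean percentage change from baseline.

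| CV | Readings | Mornings repeated | No true change: highest | No true change: averaged | Difference | True −20%: highest | True −20%: averaged |
|---|---|---|---|---|---|---|---|
| 5% | 2 | 10% | +0.7 | +0.4 | 0.3 | −19.5 | −19.8 |
| 5% | 2 | 30% | +1.2 | +0.3 | 0.9 | −19.1 | −19.8 |
| 5% | 3 | 10% | +0.8 | +0.4 | 0.4 | −19.4 | −19.8 |
| 5% | 3 | 30% | +1.7 | +0.4 | 1.3 | −18.7 | −19.7 |
| 10% | 2 | 10% | +1.0 | +0.4 | 0.6 | −19.3 | −19.8 |
| 10% | 2 | 30% | +2.0 | +0.3 | 1.7 | −18.4 | −19.8 |
| 10% | 3 | 10% | +1.3 | +0.4 | 0.9 | −19.0 | −19.7 |
| 10% | 3 | 30% | +3.0 | +0.4 | 2.6 | −17.6 | −19.7 |
| 10% | 2 | all | +6.0 | +0.4 | 5.6 | −15.2 | −19.7 |
| 10% | 3 | all | +8.9 | +0.3 | 8.6 | −12.9 | −19.7 |

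With 10% to 30% of mornings repeated, the difference due to the rule runs from 0.3 to 2.6 points, and five of the eight cases lie between 0.5 and 2. The small positive values left under averaging come from dividing by a noisy baseline, not from the repeat rule. The simulation averages over mornings. With a constant repeat rate, the expected shift in a single day's summary is the same.

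**Comparison with placebo.** With equal repeat rates, the active-to-placebo ratio stays at 0.80 under either rule when the true ratio is 0.80. With two readings and repeats on 30% of active but 10% of placebo mornings, it moves to 0.81 (CV 10%) or 0.82 (CV 20%).

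**The case against.** The strongest reply is that the rule may hardly ever operate. Home FeNO is scheduled morning and evening, and neither document plans replicate home readings. Where several attempts are intended, as for PEF in Protocol 8.1.11, the protocol says so. This stands: the size is conditional on an unknown repeat rate.

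It is also fair that neither form of the stated Part 1 endpoint (SAP 3.2.5: Day 28 and the treatment-period average) is clearly affected. Day 28 is a clinic visit, where repeats are averaged. The home period average may be built from all readings without the maximum. The output plainly affected is the by-day home summary, which falls mainly after the residential stay of at least two weeks. The three FeNO figures in SAP 4.13.2 are all in-clinic.

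A reader might infer three stronger things, and the documents do not support them:
- *That a real FeNO reduction would be hidden.* At a CV of 5% to 10% with 10% to 30% of mornings repeated, a true 20% fall still shows as 17.6% to 19.5%. Even with three readings every morning at a CV of 10% it shows as 12.9%. Only a reduction about as small as the shift itself could disappear.
- *That the comparison with placebo is biased.* The rule applies to every arm, so the shift cancels in expectation unless repeat rates differ.
- *That the rule makes home and clinic FeNO non-comparable.* They already differ in setting and in baseline definition (SAP 4.6.1), and averaging repeats would not remove those differences.

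Finally, SAP version 5.0 was prepared for anticipated closure, after unblinded Part 1 safety reviews by a committee that included the sponsor study team, and FeNO is among the Part 1 safety measures. That is a reason to document a change carefully. It does not justify setting a post-baseline maximum against a baseline mean.

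**Conclusion.** The inconsistency is real and minor. Followed as written, the rule moves by-day home FeNO percentage change upward in every Part 1 arm, in sessions with unequal repeat readings. The size is about 3% to 8% per repeated session and roughly 0.5 to 2 points in the mean (0.3 to 2.6 across the cases run) if 10% to 30% of mornings are repeated. These figures rest on the assumed CV, number of readings and repeat rate. Only the direction follows from the text alone.

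The consequence is attenuation of a within-arm reduction in an exploratory, descriptive summary. Arms are small: 30 participants randomised 1:1:1 in Part 1a gives 10 per arm, and 15 randomised 2:1 in Part 1b gives 10 and 5. Repeat rates could therefore differ between arms by chance, but nothing in the documents shows that they do. In-clinic FeNO, Day 28 and all Part 2 FeNO are unaffected.

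**What to change.** In SAP 4.13.2, replace the highest-value rule for repeated home FeNO readings with their average, as for in-clinic FeNO. State that this averaged session value is also what enters the home treatment-period average, which settles the present ambiguity. SAP 4.2 has a separate rule for repeated safety assessments (first non-missing value after dosing), so a short note should say which rule governs FeNO in the safety outputs.

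The cost is a sentence or two in the SAP and a small programming change. No new data are needed and no hypothesis test changes. Under SAP section 1, the change belongs in a new SAP version before database lock or in an addendum afterwards. The date and reason should be recorded, given the earlier unblinded Part 1 reviews. Reporting how many home sessions had repeats would show whether the rule mattered at all.
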